## Outcome Measures

The primary outcome was Tinnitus severity as measured by the Tinnitus Functional Index (TFI) (Meikle et al., 2012). Secondary outcomes included measures of anxiety, depression, insomnia, tinnitus cognitions, hearing-related difficulties, and health-related quality of life. Spanish translations (Manchaiah et al., 2020b) of all outcome measures are listed below.

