### **Recruitment**

We aimed to recruit participants across the globe without any geographical barrier. To recruit Spanish speakers, a range of strategies were used to disseminate information, including social media (Facebook and Twitter), emails, forums. As uptake was low a company "TrialFacts" were contracted to boost recruitment. The main recruitment period was between 1 March to 20 April 2020. Those interested were directed to the study website, where all the information was available to read in Spanish regarding what the study entailed and how to register. Study eligibility was determined as follows:

- Spanish speakers, adults, aged 18 years and over from any location;
- Access to a computer, the internet and the ability to email;
- Experiencing tinnitus for a minimum period of three months;
- A tinnitus severity score of 25 or greater on the TFI indicating the need for an intervention;

- Not undertaking any other therapies or interventions that may interfere with the current study; and
- Not presenting with any serious health conditions that may prevent undertaking the intervention.

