### **Effect Sizes and Statistical Modelling**

Effect sizes (Cohen's  $d$ ) at post-intervention were calculated by dividing the differences in pre- and post-intervention means by the pooled standard deviations. The reliable change index (RCI) (Jacobson & Truax, 1991) was used as a means of calculating clinical significance for the TFI as the primary outcome. This was calculated using the mean pretest posttest score difference, the pre-intervention standard deviation, and a test-retest reliability coefficient of 0.78, and as reported in the validation study (Meikle et al, 2012). Finally, linear mixed models (LMM) using maximum likelihood with random intercept for participants were used to account for repeated measures and incorporate all available data points in the analysis. The models were used to determine the effect of the pre-intervention scores on follow-up scores. The LMM induces a scaled identity covariance structure. Bonferroni-corrected pairwise post hoc tests were applied to determine which timepoints were significantly different, for each variable.

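### The TFI reliable change index pairs this trial's baseline SD with a reliability from another study and is fed the group mean change, so its threshold is of uncertain validity and it does not measure clinical significance as described

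*Combined protocol and SAP*

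**What the plan says.** In the combined protocol and SAP, Effect Sizes and Statistical Modelling, the RCI "was used as a means of calculating clinical significance for the TFI as the primary outcome". Its inputs follow: "This was calculated using the mean pretest posttest score difference", then "the pre-intervention standard deviation, and a test-retest reliability coefficient of 0.78, and as reported in the validation study". The study cited for the coefficient dates from 2012.

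Two other sections bear on these inputs. Recruitment makes this an entry criterion: "A tinnitus severity score of 25 or greater on the TFI indicating the need for an intervention". Outcome Measures says that Spanish translations "of all outcome measures are listed below", citing a 2020 paper.

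The document gives no baseline SD, z multiplier, numerical threshold, rule for classifying a participant, or sensitivity analysis for the reliability. It also does not give the severity range or SD of the validation sample, or a reliability for the Spanish TFI.

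**The concern.** The RCI asks whether one person's change is larger than measurement error would explain. Its error term, SD × √(1 − r), recovers the instrument's standard error of measurement only if SD and r come from the same population. Here they come from different samples, for two reasons visible in the document. Selecting people on the scale being analysed removes its lower tail and shrinks the SD, but does not make the instrument more precise. And a coefficient published in 2012 cannot be an estimate for a translation published in 2020.

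The index is also described with the group's mean change as its numerator. A group mean compared with an individual's error band says nothing about how many people changed reliably.

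This is the only measure of clinical significance named for the primary outcome. The study has no control group, so no comparator would show how much apparent improvement is noise, and its results are meant to inform a larger randomized trial.

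**Working it through.** The plan states no threshold or count, so there is no figure to reproduce. The checks below show how far the threshold depends on the inputs.

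**Inputs from the document:** r = 0.78; SD = the trial's baseline SD (no value given); entry at TFI ≥ 25; n = 32. **Assumed:** z = 1.96, because the plan gives none for the RCI; TFI population means of 35-60 and SDs of 18-25; normal scores with constant measurement error.

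**1. Formula.** SEM = SD × √(1 − r); S_diff = √2 × SEM; threshold = 1.96 × S_diff. At r = 0.78, S_diff = √0.44 × SD = 0.663 SD, and the threshold is 1.96 × 0.663 SD = 1.30 SD. That is 19.5 points at SD 15, 26.0 at SD 20 and 32.5 at SD 25.

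**2. Restricted SD.** Suppose 0.78 holds in a population without a lower cut, and the trial takes only those scoring 25 or more. Over the assumed means and SDs, simulation gives a cut-sample SD of 0.68 to 0.94 times the uncut SD. The threshold scales with the SD, so it is 6% to 32% below the matched one.

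- Example, mean 50 and SD 22: the cut SD is about 18, so the plan's threshold is 1.30 × 18 = 23.4 points, against 1.30 × 22 = 28.6 with matched inputs.
- The reliability consistent with the cut SD would be 1 − 0.22 × 22²/18² = 0.67, not 0.78.
- If the uncut comparator is confined to the 0-100 scale, the SD ratio is 0.76 to 0.93, so the shortfall is 7% to 24%.
- If the validation sample had a similar restriction, the ratio is about 1 and the shortfall disappears.

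**3. Reliability of the version used.** With the SD held fixed, the threshold scales with √((1 − r)/0.22):

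| r | Threshold | Relative to 0.78 |
|---|---|---|
| 0.70 | 1.52 SD | 1.17 |
| 0.78 | 1.30 SD | 1.00 |
| 0.85 | 1.07 SD | 0.83 |
| 0.90 | 0.88 SD | 0.67 |

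This source has no fixed direction and can offset step 2. With an SD ratio of 0.85, a full-range Spanish reliability of 1 − 0.22 × 0.85² = 0.84 would cancel the restriction bias exactly.

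**4. Sampling error of the SD.** With n = 32, the 95% limits for an SD are √(31/χ²) at the 97.5% and 2.5% points on 31 degrees of freedom, or 0.80 to 1.33 times the estimate. A threshold built on the trial SD carries this noise as well.

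**5. Group mean as numerator.** If M is the mean change, RCI = M/(0.663 SD) = 1.51 × M/SD. This is the mean change in baseline-SD units multiplied by a constant. It adds nothing to the effect size already planned, apart from a different choice of SD, and it classifies nobody.

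**The case against.** A reader might infer that the threshold is probably too low and that too many participants will therefore be counted as reliably improved. The document does not support either step.

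The direction requires the validation sample to span a wider severity range than this trial, and nothing in the document describes that sample. The language difference could push the threshold up or down. Even the language of the validation study is an inference: the title of the cited translation paper calls its source measures English but does not name the TFI. As for the count, the SAP defines no classification of individuals, so there is no planned number to be inflated. If the rule were applied to individuals under the assumptions of step 2, 3.4-12.0% of truly unchanged people would exceed the threshold, against 2.6-3.4% with matched inputs. That describes an output the plan does not specify.

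It is also fair to say that the SAP's outcomes of interest are retention, feasibility and effect size, and that no decision rule or sample size rests on the RCI. The mention of the mean difference may be loose wording for an index meant for individuals. And the SD's sampling error at n = 32 is as large as the possible bias.

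These points limit the claim but do not remove it. The inputs still come from different samples, no range is shown, and the text as written gives an individual-level index a group-level numerator. Sampling error in the trial SD is a further reason not to rest the threshold on that SD alone.

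**Conclusion.** The concern holds in a limited form. The SD and reliability come from different samples, and possibly from different language versions, so the error term may not be the instrument's measurement error. The threshold is about 6-32% too low if 0.78 came from a sample without a similar lower cut, given the assumed means, SDs and normal scores; the shortfall from this source is nil if the validation sample was similarly restricted. Separately, a Spanish reliability between 0.70 and 0.90 would put the correct threshold between 1.17 and 0.67 times the one used. The net direction cannot be settled from the document.

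The use of the group mean does not depend on these assumptions: as written, the calculation does not measure clinical significance. The consequence is confined to how clinical benefit on the primary outcome is described. The feasibility and effect-size results are unaffected.

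**What to change.** In Effect Sizes and Statistical Modelling:

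- State the RCI formula, the z value and the resulting threshold in TFI points.
- Apply the threshold to each participant's change, and report the number and proportion reliably improved with exact 95% CIs.
- Take SD and reliability from one sample: the validation study's own SD with its 0.78. Show the result with the trial's baseline SD alongside.
- Repeat at r = 0.70, 0.78, 0.85 and 0.90.
- State that 0.78 is not an estimate for the Spanish translation.

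Reporting the internal consistency of the Spanish TFI would not repair the input, because it is not test-retest reliability.

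The cost is a few sentences, one SD looked up in a source already cited (it is not in the document), and one small table. No new data are needed. The reported share of reliable improvers may be lower.

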## Study Design

A single-group pretest posttest design was used to determine the feasibility of ICBT for Spanish communities and refine the protocol for larger studies. This was intended to be an initial small-scale study ( $n = 32$ ) without a control group to test the protocol prior to allocating resources to a larger scale study. Such studies are an important initial part of clinical trials designs for complex interventions and considered as the Phase 1 trial.

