### ***Secondary Outcome Measures***

The following secondary measures were incorporated to assess commonly reported tinnitus-related difficulties:

- The Generalized Anxiety Disorder-7 (GAD-7; Spitzer et al., 2006) assessed symptoms of generalized anxiety disorder.
- The PHQ-9 (Spitzer, Kroenke, Williams, 1999) indicated symptoms of depression.
- The Insomnia Severity Index (ISI; Bastien, Vallières, & Morin, 2001) assessed the presence of insomnia.
- The Tinnitus Cognitions Questionnaire (TCQ; Wilson & Henry, 1998) was used to measure negative tinnitus cognitions.
- The EQ-5D-5L (Herdman et al., 2011) measured general health-related quality of life.
- The Tinnitus and Hearing Survey (THS; Henry et al., 2015) was used as a short measure to identify participants' tinnitus severity, hearing disability, and hyperacusis.

To monitor participants tinnitus severity while undertaking the intervention, the screening version of the Tinnitus Handicap Inventory (THI-S; Newman et al, 2008) was completed weekly during the course of the 8 week intervention. If scores increased by more than 10 points between two consecutive weeks, the participant was contacted to discuss presenting difficulties.

Participants were also monitored weekly by a newly developed Tinnitus Qualities Questionnaire (TQQ; Beukes et al., 2021a). The TQQ measures psychoacoustic tinnitus qualities such as pitch, loudness, and the number of tones heard.

Online questionnaires were used throughout the study. All the measures were completed pre- and post-intervention, and at two-month follow-up. To maximize retention, 3 electronic reminders were sent to participants who had not completed questionnaires.

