### **Statistical Analysis Plan**

Statistical analyses were performed using the Statistical Package for Social Sciences (SPSS) version 26.0. The study outcomes of interest were retention, feasibility, and effect size at post-intervention. For all analyses, the goal of this pilot was to estimate the pre-post-test effect size for all primary and secondary outcomes; however 2-sided  $p$ -values using alpha = 0.05 are also reported. Missing data were handled through multiple imputation using the Markov Chain Monte Carlo approach as they were missing at random (Little's MCAR test  $X^2 = 17.50$  (24) = .83). For comparison purposes a completer's only analysis was also done. The data that support the findings of this study are openly available in Figshare at <http://doi.org/10.6084/m9.figshare.13718896>.

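### The Bonferroni correction over three timepoint pairs tests the pre-post contrast less efficiently than it need be (low priority)

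*Combined protocol and SAP*

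**What the plan says.** All of this is in the combined protocol and SAP.

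- Secondary Outcome Measures sets three assessments: "All the measures were completed pre- and post-intervention, and at two-month follow-up".
- Effect Sizes and Statistical Modelling fits the repeated measures with "linear mixed models (LMM) using maximum likelihood with random intercept for participants were used to account for repeated measures", and then states: "Bonferroni-corrected pairwise post hoc tests were applied to determine which timepoints were significantly different, for each variable". No pair is set apart and no order of testing is given.
- Statistical Analysis Plan gives the priorities: "The study outcomes of interest were retention, feasibility, and effect size at post-intervention". It adds that "the goal of this pilot was to estimate the pre-post-test effect size for all primary and secondary outcomes", and that two-sided p-"values using alpha = 0.05 are also reported".
- Study Design describes an "initial small-scale study ( $n = 32$ ) without a control group".

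No other test of pre against post is named. Cohen's d and the reliable change index are not tests, and the mixed model is described in terms of how baseline scores bear on later ones.

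**The concern.** The plan gives priority to the change from pre to post, but its multiplicity rule treats that change as one of three equal pairs. Pre-post therefore gives up part of its alpha to pre versus follow-up and post versus follow-up, neither of which the Statistical Analysis Plan section lists among the outcomes of interest.

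Plain Bonferroni is also not the most efficient way to control the error across three pairs. In a sample of 32, an unadjusted pre-post p-value between 0.0167 and 0.05 would be reported as not significantly different because of the correction, even in some samples where a procedure with the same family error would have rejected. Only the p-values and the wording attached to them are at stake.

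**Working it through.** **Inputs from the document.** Two-sided alpha 0.05 (Statistical Analysis Plan); three timepoints (Secondary Outcome Measures); Bonferroni over all pairs within each variable (Effect Sizes and Statistical Modelling); n = 32 (Study Design). The document gives no power, target effect, SD of change, pre-post correlation or dropout, so there is no figure of its own to reproduce.

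**Assumption.** dz, the mean change divided by the SD of change, is scanned from 0.3 to 0.8.

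**Level per pair.** 3 × 2 / 2 = 3 pairs, and 0.05 / 3 = 0.0167. Comparing a Bonferroni-adjusted p-value with 0.05 is the same rule.

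**Power at each level.** Two-sided paired t test with n = 32, df = 31 and noncentrality λ = dz × √32 = 5.657 × dz. Power = 1 − T(c; 31, λ) + T(−c; 31, λ), where T is the noncentral t distribution function and c is 2.04 at 0.05 or 2.53 at 0.0167. For example, dz = 0.4 gives λ = 2.26.

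| dz | Power at 0.05 | Power at 0.0167 | Loss (points) |
|---|---|---|---|
| 0.3 | 0.376 | 0.219 | 15.7 |
| 0.4 | 0.592 | 0.407 | 18.5 |
| 0.5 | 0.782 | 0.619 | 16.3 |
| 0.6 | 0.908 | 0.800 | 10.8 |
| 0.7 | 0.970 | 0.916 | 5.3 |
| 0.8 | 0.992 | 0.972 | 2.0 |

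The largest loss is at dz of about 0.4: 18.5 points with df 31, 17.8 with the roughly 62 within-person df of the random-intercept model, and 17.2 by the normal approximation. The dz detectable with 80% power moves from 0.51 to 0.60.

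**What other procedures recover.** Simulation with 40,000 runs per scenario, n = 32, equal correlations (assumed 0.6) and the pooled within-person error. The range in each cell covers three patterns: effect kept at follow-up, halved, or lost.

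| Procedure | Pre-post power, dz 0.4 | Pre-post power, dz 0.5 |
|---|---|---|
| Bonferroni | 0.42–0.43 | 0.64–0.65 |
| Holm | 0.43–0.46 | 0.65–0.68 |
| Omnibus 5%, then unadjusted pairs | 0.47–0.53 | 0.68–0.75 |
| Pre-post first at 0.05 | 0.60–0.61 | 0.79–0.80 |

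Holm gains about 1 to 4 points. The omnibus procedure gains about 2 to 10 points over dz 0.4 to 0.6, with the smaller gains when the effect is halved at follow-up. With no effect at any timepoint, the chance of at least one false rejection was about 0.044 for Bonferroni and 0.050 to 0.051 for the omnibus procedure.

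**Why the omnibus procedure is valid.** With three means, if the global null is false, at most one pairwise equality can still be true. One test of the global null at 5%, followed by pairs at 5%, is therefore a closed test. This does not extend to four or more timepoints.

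**A limit on it.** Holm rejects everything that Bonferroni rejects. The omnibus procedure is more powerful in every scenario simulated, but not sample by sample. If the third mean lies midway between the other two, F = t²/2. A pair just at the Bonferroni limit with df 62 (t = 2.46) then gives F = 2.46²/2 = 3.03, below the 5% critical value of 3.15.

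**The case against.** The strongest reply is that little depends on this test. The stated goal is estimation, the p-values are an addition, and no power target or progression rule rests on p < 0.05. That stands, and it sets the priority.

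A reader might infer that the plan throws away 18 points of power which any sequential method would keep. The documents do not support that. Eighteen points is the worst case over an effect size they never state, and the loss is only 2 points at dz 0.8. Only a fixed sequence recovers all of it. That sequence does not dominate Bonferroni, because it leaves both follow-up contrasts untested if pre-post fails, although follow-up is a planned assessment of every measure. Weighting the three pairs equally is defensible; what is not needed is to do it by plain Bonferroni.

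A reader might also infer a contradiction between alpha of 0.05 and a test at 0.0167. There is none: 0.05 can be the threshold for Bonferroni-adjusted p-values. If separate unadjusted pre-post p-values were intended, the loss would not apply to them, but no such test is named.

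Two further objections hold. The plan is in the past tense and already reports an observed result for the missing-data test, so a more permissive order chosen now could not claim error control. And with a minimum TFI score of 25 for entry and no control group, part of any pre-post fall may be regression to the mean, which more power does not cure.

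**Conclusion.** The point holds as a matter of efficiency, not as an error. The pre-post contrast is tested at 0.0167, which costs between 2 and about 18 points of power against an unadjusted 0.05 for dz between 0.8 and 0.3, with n = 32 complete pairs. Of that, 1 to 4 points can be recovered with Holm at no cost in error control or in contrasts tested, and about 2 to 10 points with the omnibus procedure at dz 0.4 to 0.6. These gains rest on the assumed dz, and the simulated ones also on a correlation of 0.6 and equal correlations between timepoints.

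The effect sizes and the reliable change index do not move. All the procedures compared control error within one variable only, not across the primary and secondary scales. Priority is low.

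**What to change.** For this study:

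- Replace Bonferroni by Holm, or by an omnibus time test at 5% followed by unadjusted pairs. Choose one without reference to which gives the preferred result. If the choice comes after results are known, label it post hoc and keep the Bonferroni results visible.
- Report the unadjusted pre-post p-value and 95% confidence interval beside the adjusted p-value, and say which level governs the pre-post statement.
- Do not read an adjusted non-significant result as absence of change.

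This takes a sentence or two and no new data. Holm has no simple matching simultaneous intervals, which is a further reason to show the unadjusted interval. The omnibus procedure can occasionally miss a pair that Bonferroni would have caught.

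For the larger trial that this pilot is meant to inform, if the same three-timepoint comparison is carried forward, the protocol can specify in advance that the TFI pre-post contrast is tested first at two-sided 0.05, with the two follow-up contrasts tested by Holm only if it succeeds. That recovers the whole loss. The price, to be accepted knowingly, is that the follow-up contrasts go untested if pre-post fails.

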### **Sample Characteristics**

Descriptive statistics including gender, age, tinnitus duration, hearing aid use, and professionals consulted, were used to describe the sample. The mean and standard deviation were reported for each outcome measure at each time point. Descriptive statistics were also used to describe intervention adherence and engagement including the number of logins and modules read.

